9.2 SAMPLE SIZE DETERMINATION

Aim 1: There is no preliminary data for effect size estimation using the paradigm and patient population suggested in this study. The primary outcome measure in aim 1 is change in FTM.

H_0 : Mean change in Frontal midline theta power on electroencephalogram after iTBS to the medial prefrontal cortex will be equal to FMT changes after dorsolateral prefrontal cortex stimulation and stimulation of S1.

H_1 : Mean change in Frontal midline theta power on electroencephalogram after iTBS to the medial prefrontal cortex will be greater than FMT changes after dorsolateral prefrontal cortex stimulation and stimulation of S1.

I expect a medium effect size of $f^2 \geq 0.15$. With significance level set at $\alpha = 0.05$, using linear multiple regression modeling in G*Power software, with 3 predictors, an N of 45 subjects yields power of 0.82 for this crossover design. In a published study examining theta power using EEG plus iTBS at the dorsolateral prefrontal cortex in healthy adults, they found significant changes in theta power after iTBS with an N of 10 subjects⁵⁹. Therefore we propose 48 subjects for this current study, which should sufficiently power our study for the primary outcome measures.

Aim 2: Though there is no preliminary data for theta band power correlates of depression or autonomic symptoms in Parkinson's disease, there are studies that have looked at EEG spectral power correlations of cognitive symptoms in PD. In one study that contained sufficient published data to calculate power, they found a correlation between EEG spectral power and executive dysfunction in PD with an OR of 0.130 (95% CI [0.02-0.83])⁶⁰. The primary outcome measure in Aim 2a and Aim 2b is FTM. I used G*Power software to calculate sample size for a linear regression model with a significance level set at $\alpha = 0.05$ and Power = 0.80, which yielded a necessary sample size of 22 subjects. 45 subjects yields a power of 0.98 (95% confidence interval [0.24 – 0.99]). We will propose to recruit 48 subjects to ensure that our study is sufficiently powered.

Aim 2a:

H_0 : There is zero correlation between severity of autonomic dysfunction symptoms at baseline before stimulation with frontal midline theta power at baseline on electroencephalogram.

H_1 : There is a negative correlation between severity of autonomic dysfunction symptoms at baseline before stimulation with frontal midline theta power at baseline on electroencephalogram.

Aim 2b:

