Primary Analysis, Aim 2: 1. To test associations of autonomic symptoms in PD subjects with FMT, we will use linear regression modeling. The dependent variable will be FMT, whereas primary covariates will be SCOPA-AUT, OHQ score, and magnitude of systolic blood pressure reduction during orthostatic blood pressure measurement. We will further use linear regression models to examine the associations between depression symptoms in PD subjects and FMT, using linear regression modeling. **Exploratory Analyses:** 1. We will use linear mixed models to examine the effect of iTBS on autonomic symptoms one day after, and 4 days after stimulation. SCOPA-AUT and OHQ will be the dependent variable in the ANOVA analysis. The factors will be stimulation location (mPFC, DLPFC, S1) by time (before and after). 2. Similarly, we will use linear mixed models to evaluate the effect of iTBS on depression symptoms one day after, and 4 days after stimulation. BDI-II will be the dependent variable, whereas the primary factors will be stimulation location (mPFC, DLPFC, S1) by time (before and after). **In all statistical models,** Some key confounding factors (age, disease duration) will be controlled in both linear mixed effects and regression models. **Post-hoc analysis** will be performed using Tukey's method to control for multiple comparisons.

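### Section 9.2, Aim 2: the lower power limit of 0.24 does not follow from the cited odds-ratio limit of 0.83; the method that reproduces the section's other figures gives about 0.10

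*Combined protocol and SAP*

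**What the plan says.** Aim 2 is a primary objective: the correlation of frontal midline theta power with autonomic symptoms (2a) and depression symptoms (2b) at baseline. Section 9.2 of the combined protocol and SAP says that no preliminary data exist for these associations. It borrows an effect from one study of EEG spectral power and executive dysfunction in Parkinson's disease, "with an OR of 0.130 (95% CI [0.02-0.83"].

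The calculation is described as follows: "I used G*Power software to calculate sample size for a linear regression model", with "significance level set at $\alpha = 0.05$ and Power = 0.80", "which yielded a necessary sample size of 22 subjects". The section then reports that "45 subjects yields a power of 0.98 (95% confidence interval [0.24" to 0.99], and concludes: "We will propose to recruit 48 subjects to ensure that our study is sufficiently powered".

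For Aim 2 the section does not state the conversion from odds ratio to regression effect size, the number of predictors, or whether the test is one- or two-tailed. The alternative hypothesis is directional: "There is a negative correlation between severity of autonomic dysfunction symptoms at baseline before stimulation", and likewise for depression. The Aim 2a model in 9.4.1 has three symptom measures as predictors ("primary covariates will be SCOPA-AUT, OHQ score, and magnitude of systolic blood pressure reduction" on standing), with age and disease duration as confounders.

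**The concern.** The natural reading of the bracket after 0.98 is that it shows power at the two ends of the cited odds-ratio interval. The exploratory calculation in the same section is built that way. An odds ratio of 0.83 is a very weak association, and 45 subjects should detect it little more often than the 5% false-positive rate. A power of 0.24 there looks too high.

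The effect size is borrowed from a different symptom domain, so this interval is the reader's main guide to how fragile the Aim 2 power claim is. If its lower end is wrong, the assurance of sufficient power has less support than it appears to have.

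**Working it through.** **Inputs, all from section 9.2:** odds ratio (OR) 0.130, limits 0.02 and 0.83; alpha 0.05; N = 45; stated results N = 22 for 80% power and power 0.98 [0.24 to 0.99]. The conversion and sidedness are not stated, so I first looked for a method that returns the stated figures.

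**Formulas**
- d = |ln OR| × √3/π
- f² = d²/4
- Noncentrality = √(f² × N), with N − 2 degrees of freedom for one predictor
- Power from the noncentral t distribution (one-tailed) or the noncentral F (two-tailed)

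**Step 1. Reproduce the stated point figures.** For OR 0.130, |ln OR| = 2.040, d = 1.125 and f² = 0.316.
- One-tailed power is 0.799 at N = 21 and 0.817 at N = 22, so the required N is 22, as stated.
- At N = 45 the noncentrality is √(0.316 × 45) = 3.77 and one-tailed power is 0.981, as stated.
- Two-tailed, the required N is 27 and power at N = 45 is 0.958. Neither matches the text.

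**Step 2. Check that the rest of 9.2 uses the same method.** One-tailed, at N = 45:
- Aim 1, f² = 0.15, 3 predictors: 0.819 (stated 0.82).
- Exploratory aims, f² = g²/4, 2 predictors: g = 1.0 gives 0.951, g = 0.3 gives 0.256 and g = 1.7 gives 1.000 (stated 0.95 [0.26 to 1.00]).

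So the section is consistently one-tailed, and its exploratory interval is power at the limits of the cited effect-size interval.

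**Step 3. Apply the same method to the Aim 2 limits, N = 45.**

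| OR | d | f² | Power, one-tailed | Power, two-tailed | Stated |
|---|---|---|---|---|---|
| 0.83 | 0.103 | 0.0026 | 0.096 | 0.063 | 0.24 |
| 0.130 | 1.125 | 0.316 | 0.981 | 0.958 | 0.98 |
| 0.02 | 2.157 | 1.163 | >0.999 | >0.999 | 0.99 |

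Only the lower limit fails. Like for like, 0.24/0.096 = 2.5. At the planned N = 48 the one-tailed figure is 0.098.

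**Step 4. Test other routes to 0.24.**
- Fitting 3 or 5 predictors instead of 1, with the same f², moves the one-tailed value by no more than 0.0001.
- Other conversions from OR to correlation (ln OR/1.65, Yule's Y and Q, Digby, tetrachoric) give 0.09 to 0.15 one-tailed and 0.06 to 0.09 two-tailed.
- Solving backwards, power of 0.24 at N = 45 needs an OR of about 0.60 one-tailed or 0.50 two-tailed. Neither value appears in the document.
- One-tailed power at N = 45 is 0.2385 for f² = 0.02 and 0.988 for f² = 0.35, which round to 0.24 and 0.99. The bracket may therefore show power at two f² values that are not the converted OR limits. This is an inference about its origin; nothing in the text states it.

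**Step 5. Find where power reaches 0.80 at N = 45.** One-tailed, power is 0.810 at OR 0.25 and crosses 0.80 at about 0.255. Two-tailed, it crosses at about 0.21.

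**The case against.** The strongest reply is that little turns on this. A printed lower limit of 0.24 already tells the reader that power could be poor. Aim 1 proposes 48 participants before Aim 2 is discussed, and 48 exceeds the 22 needed at the point estimate. The synopsis labels the study a pilot. All of that stands, and it makes this a reporting correction.

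It is also fair that the conversion is unstated, and that reading the bracket as power at the odds-ratio limits is an inference. The exploratory interval supports that reading, and no conversion tried reaches 0.24. The uncertainty therefore widens the corrected value to 0.09 to 0.15 without rescuing the printed one.

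A reader might infer more than the documents support:
- **That an undeclared one-tailed test inflates the headline figures.** The alternatives are directional and every calculation in 9.2 reproduces one-tailed. What remains is that sidedness is not written beside alpha, while 9.4.1 plans likelihood ratio or Wald tests with 95% intervals, which are ordinarily two-sided. The two-tailed figures are conditional on that choice and do not correct an error.
- **That the worst case is overstated fourfold.** That ratio divides a one-tailed 0.24 by a two-tailed 0.063.
- **That power is adequate only near the point estimate.** One-tailed, it is at least 0.80 for every odds ratio from 0.02 to about 0.255. On the log scale that is ln(0.255/0.02)/ln(0.83/0.02) = 2.55/3.73, or about two thirds of the cited interval.
- **That the upper limit is also wrong.** The gap between 0.99 and >0.999 has no consequence.

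**Conclusion.** The printed lower limit is wrong as written. By the method that returns the section's own N of 22 and power of 0.98, power at the cited odds-ratio limit of 0.83 is about 0.10, so the worst case is overstated about 2.5-fold. At that limit the study would have little more chance of a significant result than under no association.

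The statement that 48 participants will *ensure* sufficient power therefore goes further than the cited source allows. Power falls below 0.80 for odds ratios weaker than about 0.25, and the cited interval extends to 0.83.

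The conclusion assumes that the bracket means power at the odds-ratio limits, that the test is one-tailed on a single coefficient, and that the conversion is d = |ln OR| × √3/π with f² = d²/4. The first is inferred from the exploratory calculation; the other two are inferred from reproducing the stated figures. The power of 0.98 stands if the test is one-tailed, and nothing here calls for a larger sample.

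**What to change.** Edit the Aim 2 paragraph of section 9.2:
1. State the conversion from odds ratio to f² and the sidedness of the test.
2. Restate the result as: *one-tailed alpha 0.05, N = 45, power 0.98 (0.10 to >0.99 across the cited 95% CI of the odds ratio)*.
3. Only if the Aim 2 test will be two-sided, give instead power 0.96 (0.06 to >0.99) and N = 27 for 80% power.
4. Replace the assurance of sufficient power with: *with 45 subjects, power is at least 0.80 for odds ratios of about 0.25 or stronger (about 0.21 if two-sided) and falls below that for weaker associations, up to the cited limit of 0.83*.

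The cost is a few sentences and a less favourable interval. Sample size, design and analysis model are unchanged.

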9.3 POPULATIONS FOR ANALYSES

We will use a modified Intention-to-Treat Analysis Dataset (e.g. participants who at least started the stimulation, whether or not they were able to complete the stimulation session, and/or sufficient follow-up outcome data).

9.4 STATISTICAL ANALYSES

9.4.1 GENERAL APPROACH

All data are double entered by independent keyboard operators, compared to identify discrepancies, then reconciled with the data manager. All datasets are backed up daily. Linear mixed models with repeated measures across different regions or over time will be the primary analytic tool for testing our *a priori* hypotheses. To model correlation among repeated measures, we will primarily consider either random intercept or AR(1). We will use the likelihood ratio test (or Wald test) statistic to test

the hypotheses. We will appropriately handle missing data (e.g., missing responses and/or covariates) by using imputation or other methods. To identify significant component terms in each of the models, we will examine the parameter estimates, 95% confidence intervals, and p-values of the component terms in an analysis of fixed effects for the final mixed models. Before undertaking statistical modeling, we will perform descriptive analyses and examine the distributions of all measures. Appropriate transformations or nonparametric statistical tests will be considered if necessary. **All statistical estimates of population parameters will be tabulated along with corresponding confidence intervals (CIs) and/or standard errors (SEs) to convey levels of precision / imprecision.** Following is a detailed plan for testing each hypothesis and the power assessment when feasible.

Descriptive statistics: Categorical data (sex) will be presented as percentages. Continuous data (age, disease duration, scores on SCOPA-AUT, OHQ, BDI-II, MDS-UPDRS all parts, freezing of gait questionnaire, Epworth Sleepiness scale, REM sleep behavior disorder questionnaire, and MoCA, will be presented as means with standard deviation and range.

Primary analysis, Aim 1: To test the degree of change in the power of FMT before and after iTBS at each location, we will use linear mixed models with FMT being the dependent variable. We will primarily include stimulation location (mPFC, DLPFC, S1), time (before, after stimulation), and the interaction term Location*time in the model.

Primary Analysis, Aim 2: 1. To test associations of autonomic symptoms in PD subjects with FMT, we will use linear regression modeling. The dependent variable will be FMT, whereas primary covariates will be SCOPA-AUT, OHQ score, and magnitude of systolic blood pressure reduction during orthostatic blood pressure measurement. We will further use linear regression models to examine the associations between depression symptoms in PD subjects and FMT, using linear regression modeling. **Exploratory Analyses:** 1. We will use linear mixed models to examine the effect of iTBS on autonomic symptoms one day after, and 4 days after stimulation. SCOPA-AUT and OHQ will be the dependent variable in the ANOVA analysis. The factors will be stimulation location (mPFC, DLPFC, S1) by time (before and after). 2. Similarly, we will use linear mixed models to evaluate the effect of iTBS on depression symptoms one day after, and 4 days after stimulation. BDI-II will be the dependent variable, whereas the primary factors will be stimulation location (mPFC, DLPFC, S1) by time (before and after). **In all statistical models,** Some key confounding factors (age, disease duration) will be controlled in both linear mixed effects and regression models. **Post-hoc analysis** will be performed using Tukey's method to control for multiple comparisons.

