1 PROTOCOL SUMMARY

1.1 SYNOPSIS

Title:	Investigating Central Neurophysiologic Correlates of Non-motor Symptoms of Parkinson's Disease
Study Description:	This is a randomized, single-blinded, triple crossover study with 3 one-day iTBS, separated by a wash-out period of 3 weeks ¹ , sufficient for physiologic effects of one session of iTBS to return to baseline. Participants will undergo accelerated iTBS to 3 brain regions: medial prefrontal cortex (mPFC) (experimental site), dorsolateral prefrontal cortex (DLPFC) (alternative experimental site), or primary sensory cortex (S1) (control site). Participants will complete symptom questionnaires, neurologic examination and cognitive assessments, and orthostatic vital signs recording before and after each brain stimulation session.
Objectives:	

Primary Objective: Aim 1: To determine whether iTBS to the medial prefrontal cortex (mPFC) produces more robust changes in frontal midline theta (FMT) EEG power in people with Parkinson's disease compared with stimulation at the dorsolateral prefrontal cortex (DLPFC) or the primary sensory cortex (S1). Aim 2: A. To evaluate FMT power correlations with burden of autonomic symptoms in Parkinson's

disease. B. To evaluate FMT power correlations with burden of depression symptoms in Parkinson's disease

Exploratory Objectives:

Aim 3: To evaluate the effect of iTBS on autonomic symptoms one day after, and 4 days after stimulation. Aim 4: To evaluate the effect of iTBS on depression symptoms one day after, and 4 days after stimulation.

Aim 5: To create a database of EEG and TMS data in people with PD for the purpose of future research into novel neurostimulation therapies for PD NMS

Outcome measures:

Primary Outcome Measures: Aim 1: Degree of change of frontal midline theta power on EEG after brain stimulation. Aim 2: Degree of association between autonomic symptoms and frontal midline theta EEG power; Degree of association between depression symptoms and frontal midline theta EEG power.

Exploratory Outcome measures: Aim 3: Change in SCOPA-AUT and OHQ from before to after iTBS; Aim 4: Change in BDI-II from before to after iTBS

Study Population:

Study population will be men and women of all demographic groups with Parkinson's disease age 50-90 years who do not have a diagnosis of severe dementia who reside in North Carolina.

Phase:

N/A (pilot study)

Description of

UNC Medical Center will be the only participating site.

Sites/Facilities Enrolling

Participants:

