Clinical Evaluations: The SCOPA-AUT⁵², a validated questionnaire for autonomic symptoms in PD, and the Orthostatic Hypotension Questionnaire (OHQ)⁵³, a validated questionnaire for symptoms of orthostatic

intolerance, will be administered before, and then by telephone one day after, and four days after each stimulation session. The Beck Depression inventory II (BDI-II)⁵⁴, recommended for screening and assessment of depression severity in PD⁵⁵, will be administered before, and then by telephone one day after, and four days after each stimulation. A trained research team member will administer the Movement Disorders Society Unified Parkinson Disease Rating Scale (MDS-UPDRS)⁵¹, a validated rating scale of PD symptom severity, at baseline. Participants will have orthostatic blood pressure measurement with a standard sphygmomanometer cuff before and after each stimulation session. All evaluations will be done with subjects in the “on” medication state with regards to dopaminergic medication dosing. Quantitative EEG (qEEG) recordings will be done before and immediately after each stimulation session. EEG: A high-density EEG net (128 electrodes including electrooculography electrodes; MagStim EGI, Inc.) and two submental electromyography (EMG) electrodes will be applied. Continuous qEEG recording will be performed for 8 minutes while the participant is asked to keep their eyes open and focused on a crosshairs. Sampling rate during the continuous recording will be 1 kHz with Cz as the reference and a channel between Cz and Pz as ground, using an EGI system with SDK AmpServer Pro (Geodesic, Eugene, Oregon). Intermittent theta-burst stimulation: Subjects will undergo iTBS to the mPFC, left DLPFC, and left primary sensory area in a triple cross-over study design. I will use a MagVenture MagPro X100 TMS device with active cooling coil. Stimulation location will be determined using established scalp coordinates for each stimulation location with the “10-20” international coordinate system⁴²⁻⁴⁵. For the mPFC, stimulation will be done at the Fp1 EEG electrode location, which can be calculated as along the midline of the scalp and 10% of the distance from nasion to inion. For left DLPFC, stimulation will be done at the F3 location using the Beam-F3 technique^{46,47}. For the primary sensory cortex, stimulation will be done 1.5cm posterior to the motor hotspot used for intensity calibration. Stimulation will be delivered at 80% active motor threshold. Accelerated iTBS will be performed in the reclined position to reduce symptoms of orthostatic hypotension, with subjects awake and at rest. Subjects will receive bursts of 3 pulses at 50 Hz repeated at 200-msec intervals (5Hz) for two seconds^{48,49}. The two-second trains will be repeated 20 times every 10 seconds (4 minutes total stimulation time), and followed by a 20 minute rest period. This sequence will be repeated 4 times. Behavioral effects of stimulation last at least 36 hours after one stimulation session with this protocol¹. TMS is FDA-approved for the treatment of symptoms of depression, and is a widely-used safe clinical tool.

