7.2 PARTICIPANT DISCONTINUATION/WITHDRAWAL FROM THE STUDY

Participants are free to withdraw from participation in the study at any time upon request.

An investigator may discontinue or withdraw a participant from the study for the following reasons:

- Significant study intervention non-compliance
- If any clinical adverse event (AE), laboratory abnormality, or other medical condition or situation occurs such that continued participation in the study would not be in the best interest of the participant
- Disease progression which requires discontinuation of the study intervention
- If the participant meets an exclusion criterion (either newly developed or not previously recognized) that precludes further study participation

- There are factors that, in the opinion of the PI, would place the participant at increased physical or psychological risk, or preclude the participant's compliance or completion of the study

The reason for participant discontinuation or withdrawal from the study will be recorded on the Case Report Form (CRF). Subjects who sign the informed consent form and are randomized but do not receive the study intervention may be replaced. Subjects who sign the informed consent form, and are randomized and receive the study intervention, and subsequently withdraw, or are withdrawn or discontinued from the study, will not be replaced.

Safety data will be collected on any participant that is discontinued due to an AE or SAE. Every effort will be made to complete protocol-specific follow up procedures if possible. If voluntary withdrawal occurs, the participant will be asked to continue scheduled evaluations and complete an end-of-study evaluation. Medical and psychological follow up will be coordinated by the research team as described in this protocol. The researcher will make a note to file for all withdrawals.

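### The Aim 1 mixed model names no visit-within-participant or participant-by-time term; read as a participant intercept, its Location*time test is conservative and loses power if FMT varies between visits.

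*Combined protocol and SAP*

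**What the plan says.** Section 6.1.2 fixes the data structure: "Quantitative EEG (qEEG) recordings will be done before and immediately after each stimulation session". The synopsis (1.1) describes "3 one-day iTBS, separated by a wash-out period of 3 weeks". Two readings at each of three sessions make six per participant, in three same-day pairs.

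Section 9.4.1 takes FMT itself, not its change, as the Aim 1 dependent variable: "We will primarily include stimulation location (mPFC, DLPFC, S1), time (before, after stimulation), and the interaction term Location*time in the model". On correlation it says "To model correlation among repeated measures, we will primarily consider either random intercept or AR(1". It also states: "Some key confounding factors (age, disease duration) will be controlled in both linear mixed effects and regression models". Both of those covariates are constant within a participant, so they absorb no visit-to-visit variation. Section 9.4.2 only refers back to 9.4.1.

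The plan does not state what the random intercept is grouped by, how AR(1) is indexed over the six readings, or any visit-within-participant or participant-by-time term.

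**The concern.** The Aim 1 question is whether the before-to-after change differs by stimulation site. In the data that is a difference between same-day differences. Anything that shifts both readings of a visit together cancels from it, and so does any tendency of a participant to change by the same amount at every visit.

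A single participant-level intercept represents neither feature and leaves both variances in the residual that sets the standard error. AR(1) over the six readings in time order would treat a same-day gap and a three-week gap as the same lag. At stake is power for the primary aim, lost through the choice of covariance and not through the design.

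**Working it through.** **The plan's own figure.** Section 9.2 states power 0.82 at N = 45 with f² = 0.15, α = 0.05 and 3 predictors. For a single regression coefficient, df = 45 − 3 − 1 = 41 and the noncentrality is √(0.15 × 45) = 2.60. One-sided 5% gives 0.819, which matches. Two-sided gives 0.718; joint tests of two and of three predictors give 0.604 and 0.528. The figure comes from a regression that contains no visit variance, so it cannot be adjusted for the present point. I use 80% as the reference power instead.

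**Inputs.** n = 48 and α = 0.05 (9.2); six readings (6.1.2 and 1.1); six balanced sequences (6.2). The plan does not state the sidedness of the test, so both are shown. No FMT variance components are given, so all ratios are assumptions. Let σe² be reading variance, σv² variance between visits within a participant, and σp² between-participant variance of the pre-post change.

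**Correct error.** Each same-day change contributes 2σe². A difference between two sites' mean changes therefore has variance 4σe²/n. At n = 48 its SE is √(4/48) = 0.289 σe, whatever σv² and σp² are.

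**Error used by a participant intercept.** Each participant has five within-person degrees of freedom:

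| Source | df | Expected mean square |
|---|---|---|
| Between visits | 2 | σe² + 2σv² |
| Time | 1 | σe² + 1.5σp² |
| Location by time | 2 | σe² |

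Pooled: [2(σe² + 2σv²) + (σe² + 1.5σp²) + 2σe²]/5 = σe² + 0.8σv² + 0.3σp². With σp² = 0 the SE is too large by the factor √(1 + 0.8σv²/σe²).

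**Power and type I error, participant intercept, σp² = 0, n = 48.** The pairwise effect is set so that the correct error term gives 80%: 0.817 σe two-sided, 0.723 σe one-sided. The 2-df test is likewise set to 80%.

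| σv²/σe² | SE too large by | Pairwise power, two-sided | Type I, two-sided | Pairwise power, one-sided | 2-df Location*time power |
|---|---|---|---|---|---|
| 0 | 0% | 80% | 0.050 | 80% | 80% |
| 0.1 | 4% | 78% | 0.042 | 78% | not run |
| 0.25 | 10% | 75% | 0.032 | 76% | 73% |
| 0.5 | 18% | 69% | 0.021 | 71% | 65% |
| 1 | 34% | 57% | 0.009 | 61% | 50% |
| 2 | 61% | 37% | 0.002 | 44% | 25% |

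**With σp².** If σv² = 0 and σp²/σe² = 0.5 or 1, two-sided pairwise power is 76 or 72%. With both ratios at 0.5 it is 65%.

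**If the intercept is per participant-visit.** The residual is (3σe² + 1.5σp²)/3 = σe² + 0.5σp². Power is 80% at any σv² when σp² = 0, but 73 or 66% at σp²/σe² = 0.5 or 1.

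**If AR(1) runs over the six readings in time order.** With participant variance equal to σe², two-sided pairwise power is 80, 77, 74, 69 and 58% at σv²/σe² = 0, 0.25, 0.5, 1 and 2, with type I error from 0.058 down to 0.020. With participant variance 4σe², power is 82, 79, 76, 70 and 60%, with type I error from 0.073 down to 0.028.

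**Fitted-model check.** REML fits with a Wald test of the 2-df interaction (800 simulated trials per setting, σp² = 0) gave the following power at σv²/σe² = 0, 0.5, 1 and 2:

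- participant intercept: 0.79, 0.67, 0.52, 0.26
- AR(1): 0.81, 0.75, 0.68, 0.55
- participant plus visit intercepts: 0.81, 0.83, 0.79, 0.80

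Adding a participant slope for time also removes σp² from the error. The error term is then σe² on 2 × 47 = 94 df, and pairwise power is 80% with type I error 0.050 at σv² = σp² = σe².

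**The case against.** The strongest reply is that section 9.4.1 is under-specified, not wrong. Its wording is tentative and the intercept's level is open. No FMT variance component is available, and at ratios of 0 to 0.1 the loss is at most 2 points. Under a participant intercept the error is on the safe side, in a study that calls itself a pilot. Most of this stands: participant level is an inference, and the large losses need ratios that nothing in the documents supports or excludes. But no alternative structure is named, and the most natural reading is sound only if both extra variances are zero.

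A reader might infer three stronger things that the documents do not support.

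- **That the stated 0.82 leaves little reserve.** It comes from a different model and matches only as a one-sided test of one coefficient. The same formula gives 0.84 at the planned 48. Visit variance cannot be subtracted from it.
- **That the primary test is biased or prone to false positives.** Under a participant intercept, type I error falls below 5%. AR(1) can be slightly liberal when participant variance is large and visit variance small, but that assumes an ordering of the readings that the plan does not state.
- **That a change-score analysis should replace the model.** Section 9.2 does say "The primary outcome measure in aim 1 is change in FTM", but sections 8.1.2 and 9.1 also name FMT power itself. Sections 2.3.1 and 8.2 allow a session to be stopped early, and section 9.3 keeps "participants who at least started the stimulation, whether or not they were able to complete the stimulation session". Visits with only a pre reading are therefore foreseeable, and a change score discards them. I assumed about 10 to 20% of post readings missing at one site, more often when the pre reading is high, with σv² = σp² = 0.5σe². The change-score contrast was then biased by roughly 0.02 to 0.13 reading-SD, against under 0.02 for a correctly specified six-reading model. If missingness is unrelated to FMT, neither is biased.

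**Conclusion.** The point holds in conditional form. Neither structure named for Aim 1 represents three same-day pairs. On the participant-intercept reading, the Location*time test uses σe² + 0.8σv² + 0.3σp² where σe² is correct. It is conservative whenever either extra variance is above zero. The 2-df test loses more than a single contrast. Time-ordered AR(1), if that is meant, also loses power when visit variance is large, but less.

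The mechanism is certain given the reading; the size is not, because it rests on assumed variance ratios, 80% reference power and complete data. The Tukey adjustment in section 9.4.1 is not modelled. This is an efficiency problem in the primary analysis, not a threat to its validity, and it should be fixed because the remedy is only wording.

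**What to change.** Keep location, time and Location*time on all six readings, with age and disease duration as planned. For Aim 1 in section 9.4.1, replace the choice between a random intercept and AR(1) with:

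*Random intercepts for participant and for visit within participant, and a participant random slope for time.*

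Add, as a sensitivity analysis, a model of the three post-minus-pre changes with location fixed and participant random. In complete data it is equivalent for the location contrast. It should not replace the main model, because it discards visits with only a pre reading.

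The cost is a little more model fitting. A variance component may be estimated at zero, and the plan should say that the term is then dropped. No new data, visits or participants are needed.
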